10.4 Handling of missing data and drop-outs

Missing data will be monitored closely and queries generated back to the responsible study site for completion as much as possible.

Missing values due to lack of compliance or patient dropout from the study should remain within the expected minimum. Nonetheless, data analysis will be completed with and without missing data imputation to assess the robustness of the results.

11. QUALITY ASSURANCE AND CONTROL

11.1 Data handling and record keeping / archiving

11.1.1 Case Report Forms

Source data includes all information in original records, observations, or other activities necessary for the reconstruction and evaluation of the documentation process for this study. Samples of source data include, but are not limited to, medical history information, demographics, informed consent, patient identification number, questionnaire responses and outcome scores.

Source data are entered by the study staff, physicians and patients either on paper CRF / source worksheets (WS) or electronically into eCRFs web-based Electronic Data Capture system (REDCap)². Patients are invited to enter study questionnaires electronically, either on a tablet computer at the clinic or from home after invitation by email with an electronic link to the relevant eCRF. Alternatively they will complete paper-based CRFs.

In addition, selected patient demographics and surgical parameters may be imported into REDCap from the patient information system as requested by respective study sites.

11.1.2 Record keeping / archiving

All materials pertaining to the study, including completed WSs and paper CRFs, will documented into a Trial Master File by the study coordinator, sorted and kept in closed archives at the Research and Development Department of the Schulthess clinic.

Each study site will maintain a study Investigator Site File (ISF) to document local study procedures. All study data must be archived for a minimum of 15 years after study termination or premature termination of the clinical trial.

11.1.3 Imaging data

Imaging data of the participants will be collected and stored at each study center locally as part of the clinical routine when screening the eligibility of the patients. In the final monitoring process, all collected imaging data will be evaluated at each study center and exported as pseudonymized data.

11.2 Data management

11.2.1 Data Management System

Study data will stored into the REDCap web-based Electronic Data Capture system ² that is hosted on a dedicated server maintained by the IT department at the Schulthess clinic.

New software releases are installed after being tested by an IT support person, according to a check list of tasks that the system should perform successfully.

11.2.2 Data security, access and back-up

The REDCap study database is password protected and only accessible to dedicated personnel after signing a confidentiality form. Data exported from REDCap for the analyses are saved into a dedicated server only accessible to designated researchers.

Data security and confidentiality rules of the Schulthess clinic applies to all involved personnel.

The IT department of the Schulthess clinic is responsible and perform back-up procedures of all collected and transformed data according to internal rules.

11.2.3 Analysis and archiving

Study data is exported from the REDCap data management system in csv text file format before being imported into Stata software (StataCorp LP, Texas USA) for statistical analyses. For archiving see section 12.1.3.

11.2.4 Electronic and central data validation

At the time of data entry into the paper-based clinical report form (CRF), working sheets or electronic clinical report form (eCRF) the responsible person checks the completeness and consistency of the collected data. The utilized electronic data capture system (eDCS) (REDCap²) allows minimizing data entry error by development of branching logics and online data checks (e.g. range checks).

The statistician performs data quality control per query as appropriate to ensure the quality and integrity of the data. All queries related to a specific analysis are resolved before the final analyses can be performed. Variables required for the analyses are transformed or created after data transfer into Stata and saved in the final analysis dataset.

Data centralization and statistical analysis procedures are fully documented by the Stata programming files.

11.3 Monitoring

Study monitoring will be described in a monitoring manual. Each site will be visited at least twice, i.e. for an initiation visit (kick-off meeting) before recruiting the first patient and for a closure visit after the last patient follow-up. This will ensure understanding and standardization of study procedures as well as the integrity of the recorded data. Onsite monitoring visits will be performed only if deemed necessary for the success of the study. Project monitoring visit or closure will involve validating a defined random sample of source documents, as well as checking the appropriate management and maintenance of essential documents. This will be performed by the designated study coordinator.

The local study coordinator on each study site will check the data entered in the CRF or eCRF for each individual case with regard to completeness, plausibility and consistency. Original paper CRFs are to be regarded as documentary evidence. All entries must be made accordingly, and any alteration must be entered as an addition with explanatory note, date and signature. Electronic data entry will be performed on each study site and sites will have access only to their own case data.

The main study coordinator and project statistician will have access to all study data. They will perform regular data checks and generate queries back to the responsible site for clarification and data correction as appropriate. The investigators agree to allow the study coordinator direct access to all relevant documents and to allocate his/her time and the time of his/her staff to discuss findings and any relevant issues. This will include ensuring all data entry into the eDCS is complete and consistent with all enrolled subjects. Inconsistencies will be resolved throughout the study.

The statistician performs data quality control per query as appropriate to ensure the quality and integrity of the data. All queries related to a specific analysis are resolved before the final analyses can be performed. Variables required for the analyses are transformed or created after data transfer into Stata and saved in the final analysis dataset. Data centralization and statistical analysis procedures are fully documented by the Stata programming files.

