6.2.1 Randomisation

A randomization sequence will be generated electronically using Stata (StataCorp LP, Texas USA) separately for each participating centers for up to X patients and loaded within an online study database in REDCap² (Research Electronic Data Capture) for automatic concealed allocation. Block-randomization with blocks of 2 and 4 will be used to minimize the risk of unequal group sizes. The randomization process allows to divide the study participants into two cohorts of comparable characteristics. We will compare these cohorts with regards to potential confounding factors before the outcome analyses and adjust statistically for any observed imbalance as appropriate.

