8.4 Compliance with study intervention

The intervention (EMS or physiotherapy) will be logged in the REDCap database to ensure that the patient got the correct intervention. There are no reasons to withdrawn a patient from the study. The patient can drop-out any time from the study. The PI is in charge to collect as much data as possible from withdrawn patients (e.g. telephone call, Email); patients who withdraw from the study will not be examined.

Withdrawn patients will not be replaced.

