11.5 Confidentiality, Data Protection

During this study, medical information from included patients will be treated in strict confidence and shall not be disclosed to third parties. Confidentiality will be ensured through anonymization of the clinical results in the scientific presentations and publications. The patient identification will be known only at respective study site by authorized personnel who are bound to confidentiality.

Direct access to source documents will be permitted for purposes of monitoring, audits and inspections. Access to REDCap will be allowed only to the study team, and analyses files will accessible by the study team on the dedicated server at the Research and Development Department.

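### Section 11.3 gives the statistician unrestricted data access, arm included, while queries are raised and the primary model is still open; exports coded A/B until a dated freeze would close this gap

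*Protocol*

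**What the plan says.** On access, Protocol 11.3 (Monitoring) says: "The main study coordinator and project statistician will have access to all study data". No exception is made for the allocation.

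On queries, the same section continues: "They will perform regular data checks and generate queries back to the responsible site for clarification and data correction as appropriate". It adds for the statistician: "The statistician performs data quality control per query as appropriate to ensure the quality and integrity of the data". Section 10.4 asks for missing data to be followed up, with "queries generated back to the responsible study site for completion as much as possible".

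On where the arm is held, section 6.2.1 has the randomisation sequence "loaded within an online study database in REDCap² (Research Electronic Data Capture) for automatic concealed allocation", and section 8.4 says: "The intervention (EMS or physiotherapy) will be logged in the REDCap database to ensure that the patient got the correct intervention".

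On analysis files, section 11.5 says that "analyses files will accessible by the study team on the dedicated server". Section 11.2.2 limits exported data to designated researchers. Neither section gives a date before which by-arm files stay closed.

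On masking, section 6.2 holds that examiners need not be blinded because the main outcome is subjective, and that patients cannot be. It does not mention data review or analysis.

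On the primary analysis, section 10.3.2 allows either an independent-samples t-test or a linear regression with baseline factors, according to whether adjustment is needed. It names no factors and no criterion. Section 6.2.1 places the comparison of groups on confounders ahead of the outcome analyses.

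**The concern.** The trial is open to patients and examiners, and its primary endpoint is a self-rated score. Data review and analysis are therefore the steps at which masking is still feasible, and the protocol does not use it there. The statistician can see WOSI next to the arm while raising queries and while the form of the primary test is undecided.

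Two things are at stake. First, which values get queried could depend, even unintentionally, on arm and score. A correction leaves a record; the decision not to query a value does not. Second, if the result by arm is visible before the model is settled, the judgement on whether adjustment is needed can be influenced by the answer it gives. In an open trial with a subjective endpoint, a critical reader will ask about both, and the protocol as written has no reply.

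**Working it through.** **Is the arm within the access granted?** This is an inference, but a firm one. Section 11.3 grants all study data. Section 6.2.1 loads the allocation sequence in REDCap and section 8.4 logs the treatment received there. The concealment in 6.2.1 concerns allocation at entry, not later viewing. No section withholds the arm from the statistician.

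**Is the model open during that access?** Section 10.3.2 gives two forms of analysis and no rule for choosing. Sections 6.2.1 and 10.3.1 make baseline imbalance the trigger, judged by standardized differences, but give no threshold or covariate list. The comparison is placed ahead of the outcome analyses, yet no text bars a look at WOSI by arm before it.

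**The plan's own figures (10.2).** Effect size d = 10.4/13 = 0.8. For a two-sided t-test at 5% with 26 per arm, the noncentrality is 0.8 × √(26/2) = 2.88 on 50 degrees of freedom, which gives power 80.7%. So N = 52 reproduces as a two-sided calculation (the one-sided t-test would need 42). Dropout: 52/0.80 = 65, stated as 66. Screening: 66/0.75 = 88. Masking changes none of these.

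**How much could the open choice matter?** The following was simulated:
- 20,000 trials with no true effect, 26 per arm, two-sided 5%.
- One standard normal baseline covariate, correlated with the outcome at an assumed 0.3, 0.5 or 0.7 (the protocol gives no value).
- In each trial, the t-test and the one-covariate regression were both fitted, and a rejection was counted if either was significant.

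| Assumed correlation | t-test alone | Adjusted alone | More favourable of the two |
|---|---|---|---|
| 0.3 | 5.1% | 5.0% | 6.5% |
| 0.5 | 5.1% | 5.2% | 7.5% |
| 0.7 | 4.7% | 4.9% | 8.0% |

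The simulation standard error is at most √(0.08 × 0.92/20,000) = 0.2 percentage points. By symmetry about half of each figure falls in favour of EMS: roughly 3.2% to 4.0%, against 2.5%. Either model fixed in advance stays at about 5%. The simulation has no centre effect and assumes that the better result is always taken, so it is a ceiling for this two-model choice and not a forecast.

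**Selective querying.** The documents give nothing from which a size could be computed.

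**The case against.** The strongest reply is that the protocol is silent here rather than wrong. Masking of the statistician, the data freeze and the covariate list often sit in a statistical analysis plan, which is not at hand, and 11.3 refers to a monitoring manual. That stands in part: such documents may already settle the model. But the unrestricted access in 11.3 and the undated file access in 11.5 are statements of this protocol and would still need qualifying.

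Several stronger readings are tempting, and the text does not support them:
- *That the coordinator and statistician decide which scores are completed or corrected.* They raise queries. Patients complete the questionnaires themselves (3.1), and sites make corrections.
- *That changes leave no trace.* Section 11.3 requires alterations to be added with a note, date and signature, and analysis steps to be documented in Stata files. Only the choice of what to query goes unrecorded.
- *That the coordinator helps choose the model.* No section says so, and none names who chooses.
- *That imputation and analysis sets can be picked at will.* Section 10.4 runs the analysis with and without imputation, and 10.3.1 puts intention-to-treat first.
- *That a late WOSI would be given after the other therapy has begun.* Section 8.3 opens crossover only after the 3-month examination.
- *That everyone can open the exports.* Section 11.2.2 limits them to designated researchers.
- *That the inflated error rate is caused by access.* It comes from the open model choice. Prespecifying the model removes it whether or not anyone is masked.

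Nor is masking feasible for every task. The coordinator validates source documents, and the intervention log exists to confirm that the right treatment was given. Removing the arm entirely would also block the baseline comparison and the per-protocol set in 10.3.1.

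**Conclusion.** The point holds in a limited form. The protocol gives the statistician all data, from which the arm is not excluded, during querying and while the t-test-or-regression choice is open. It does not protect that choice from sight of WOSI by arm. The baseline check ahead of outcome analyses and the documented alterations reduce the risk without removing it.

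The size is a worst case of about 6.5% to 8% two-sided type I error against 5%. It rests on one covariate, correlations of 0.3 to 0.7, no centre effect and consistent selection of the better result. It measures the open model choice, against which masking is a second line of defence. Nothing in the documents suggests that such selection is intended. This is a desirable improvement and does not threaten the trial's validity on its own.

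**What to change.** In 11.3 and 11.5, state that:
1. The statistician's exports carry a dummy arm code (A/B), and session type is recoded as given as allocated or not. The baseline comparison and the per-protocol set can then still be built.
2. The code is broken only after queries on the 3-month WOSI are closed and the analysis sets, covariates and imputation model are frozen and dated. No 3-month WOSI is summarised by code before that date, because A/B labels hide which arm is EMS but not which model gives the smaller p-value.
3. Central queries on WOSI are raised from listings without the arm.
4. By-arm analysis files stay closed to site investigators until the last 3-month WOSI is in.
5. The study coordinator's source-document checks stay unmasked.

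The cost is a few sentences and a recoded export. An existing data-management role must hold the code. Sample size and patient procedures do not change.

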11.4 Audits and Inspections

There is no plan for auditing the study, nevertheless the study documentation and especially the source data/documents are accessible to auditors/inspectors (panel of independent

international experts) and questions will be answered during possible inspections. In this process, all involved parties must keep the patient data strictly confidential.

11.5 Confidentiality, Data Protection

During this study, medical information from included patients will be treated in strict confidence and shall not be disclosed to third parties. Confidentiality will be ensured through anonymization of the clinical results in the scientific presentations and publications. The patient identification will be known only at respective study site by authorized personnel who are bound to confidentiality.

Direct access to source documents will be permitted for purposes of monitoring, audits and inspections. Access to REDCap will be allowed only to the study team, and analyses files will accessible by the study team on the dedicated server at the Research and Development Department.

12. PUBLICATION AND DISSEMINATION POLICY

The results of the trial will be presented in a manuscript according to the CONSORT guidelines and published in a peer-reviewed journal. To ensure general availability, the publication will be made open-access. To improve dissemination and visibility the trial results will be presented at national and international shoulder conferences.

